2.2. Sample Size

It is not the remit of this Phase I trial to recruit a sufficient number of participants to be statistically confident about the differences between groups. By the end of this study 8 participants will have been randomised to each method of delivery.

2.3. Analysis datasets

The statistical analysis will be conducted on randomised participants on both an Intention-to-Treat (ITT) and a Per-Protocol (PP) basis. This is a phase I trial concerned with both safety and efficacy, ITT provides estimates of effectiveness in a 'real-world' setting where participants missed doses or became lost-to-follow-up, PP estimates efficacy under ideal conditions.

- Intention-To-Treat (ITT) dataset: all participants randomised and given at least one immunisation in the trial.
- Per-Protocol (PP) dataset: all participants randomised and immunised with all scheduled immunisations, completing the trial with no major protocol deviations.

A safety analysis population is also defined as all participants receiving at least one dose of trial medication.

2.4. Missing Data

The level and pattern of missing data on the primary immunogenicity outcome will be described in tables 1 to 3 of the statistical report.

3. Endpoint Definitions

3.1. Primary Endpoints

3.1.1. Safety

Any of the following events occurring between week 0 and week 22 will be included in the analysis:

- Grade 3 or above local solicited adverse event (Table 2)
- Grade 3 or above systemic clinical and laboratory solicited adverse event (Table 2)
- Any grade of adverse event that results in a clinical decision to discontinue further immunisations
- Any grade of adverse event within 7 days of receiving intradermal and standard intramuscular vaccinations with or without electroporation

Table 2: Solicited adverse events

Type	Event
Local AEs (immunisation site)	Discomfort Redness Swelling (soft) Induration (hard) Blisters
Systemic Clinical AEs	Abnormally raised temperature Chills Myalgia/flu-like general muscle aches Malaise (excess fatigue) Headache Nausea Vomiting
Systemic Laboratory AEs	Abnormalities in: Creatinine, AST, ALT, alkaline phosphatase, total bilirubin, glucose, Hb, total WCC, neutrophils, lymphocytes, platelets

3.1.2. Immunogenicity

The primary immunogenicity endpoint is the titre of systemic CN54rgp140-specific IgG antibodies measured 2 weeks \pm 3-day window after a participant's scheduled final vaccination (any exception to the 3-day window to be discussed by the TMG). Responses are measured using a semi-quantitative sandwich ELISA assay and defined as positive when exceeding mean OD at 450nm plus 3 SDs at a 1/100 dilution for a panel of serum samples obtained from 20 HIV negative volunteers. Samples deemed "response positive" are analysed further in a titration assay where samples are subsequently diluted to achieve at

least two OD at 450nm values that fall on the linear part of the relevant human IgG or IgA standard curve of known concentration. These values are interpolated automatically by the ELISA software (SoftMax Pro v 5.4) to give two extrapolated values in $\mu\text{g/ml}$. The mean of these 2 values is then reported as the “titre” of antigen specific IgG or IgA for response detected samples.

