6.1.5 Dose Modifications and Discontinuation

There are no planned modifications to dose, other than discontinuation.

The schedule may be modified if a participant has symptoms or signs on the day of scheduled immunisation, and the investigator considers it best to defer the immunisation. The participant will be asked to return for review within the window period of the scheduled immunisations (-3/+7 days from week 4, 8 and 20 for the second, third and fourth immunisations respectively).

A clinical investigator may decide to permanently discontinue dosing in a participant who has received one or more immunisations, if the investigator deems that continuing might compromise participant wellbeing or interfere with the achievement of the trial's objectives. Such a decision should only be taken in consultation with the Chief Investigator. Participants will be encouraged to continue to attend trial visits for sampling and safety monitoring.

Discontinuation of dosing is essential following a grade 3 or 4 clinical or laboratory event (confirmed on examination or repeat testing respectively) which is considered possibly, probably or definitely related to the vaccine and which did not resolve within 72 hours.

Provided the participant agrees they will continue to be followed up for the duration of the study and samples will be collected at the allotted times.

Dosing must be discontinued in participants who become pregnant or HIV infected.

Participants may decide to discontinue dosing. They will be encouraged to provide a reason, and to remain in follow-up. The appropriate CRF should be completed as soon as possible if a patient chooses to stop receiving vaccines or to withdraw from the trial, and within 24 hours of a decision being taken to discontinue a participant when that decision is informed by an adverse event (**section 8.1**).

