7.1.2 Visit Windows

The second, third and fourth immunisation visits scheduled for weeks 4, 8 and 20 will be compliant with the protocol if they take place ± 3 days either side of the target date determined by the date of the previous vaccination. If there is a delay >4 weeks a decision will be made by the trial management group (TMG see **section 16.1**) as to whether immunisation will continue.

The post-immunisation safety visits scheduled for weeks 1, 5 and 9 will be compliant with the protocol if they take place -3 to +7 days of the target date determined by the date of the previous vaccination. The safety visit at Week 21 will be compliant with the protocol if it takes place -3 to +3 days of the target date.

The primary endpoint and follow-up visits scheduled for weeks 22 and 24 will be compliant with the protocol if they take place ± 3 days either side of the target date determined by the date of the fourth vaccination.

The follow-up visit scheduled for week 44 will be compliant with the protocol if it takes place ± 14 days either side of the target date determined by the date of the fourth vaccination.

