5 Immunisation should be after completion of the other procedures scheduled for that visit except for the AE assessment and injection site inspection which will be conducted before and after each immunisation

6 After the first vaccination the timing of all visits is determined by the date of the preceding vaccination

7 Pre-dose and again at 10 (+/-2) min and 60 (+/-10) min post-dose; subjects are free to leave after the 60 min post-dose assessment unless otherwise indicated by AEs etc.

8 Volunteer invited back to clinic for assessment if reporting grade 3 AE or above

9 The tolerability questionnaire should be completed post-vaccinations 1–3 only

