10.2.1.2 Immunogenicity

- The magnitude of antigen specific systemic IgG antibody binding responses (µg/ml) 2 weeks after the final vaccination.

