16. TRIAL COMMITTEES

16.1 Trial Management Group (TMG)

The Trial Management Group (TMG) will be formed of the Chief, Principal and other lead Investigators (clinical and non-clinical) from the clinical centre and immunology laboratory as well as members of MRC CTU.

The TMG will be responsible for the day-to-day running and management of the trial and will be accountable to the Sponsor.

The TMG will also be responsible for the composition of the expert panel to review any emergent SUSARs.

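### SAP 3.1.2 leaves day zero of the primary IgG sample open to two readings; on one of them a boost deferred 4 or more days puts a correctly timed sample outside the window

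*SAP*

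**What the plan says.** **SAP.** Section 3.1.2 defines the primary immunogenicity endpoint as the IgG titre 2 weeks, with a 3-day window, "after a participant's scheduled final vaccination (any exception to the 3-day window to be discussed by the TMG". It gives no criteria for that discussion. Section 4.3 judges the week-22 visit against a scheduled date too, but allows ±7 days, and it states no window for the week-20 dose. Section 4.5.2 then analyses the titre at 4 weeks.

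**Protocol.** Section 10.2.1.2 puts the endpoint "2 weeks after the final vaccination", without the word 'scheduled'. Section 7.1.2 allows ±3 days for week 22 around a "target date determined by the date of the fourth vaccination". Footnote 6 to Table 5 is general: "After the first vaccination the timing of all visits is determined by the date of the preceding vaccination".

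**Movement of the boost.** Protocol 7.1.2 and Table 5 give ±3 days for dose 4. Protocol 6.1.5, on deferred doses, gives -3/+7 "days from week 4, 8 and 20 for the second, third and fourth immunisations respectively". For longer delays, 7.1.2 says: "If there is a delay >4 weeks a decision will be made by the trial management group".

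**Who decides.** Under protocol 16.1 the TMG is made up of the Chief, Principal and other "lead Investigators (clinical and non-clinical) from the clinical centre and immunology laboratory", together with members of the trials unit. Protocol 5.2 says that clinical staff know the allocation and that assay staff do not.

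**The concern.** The endpoint is meant to be the response 2 weeks after the protein boost. The protocol books the visit from the day the boost was given. If the SAP's day zero is the planned date, the two clocks separate as soon as the boost moves. A sample drawn exactly when the protocol asks can then fail the SAP's definition of the primary measurement.

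Whether that value is used would depend on a discussion with no stated rule, among people some of whom know the arm. At 8 per arm each such decision concerns one eighth of an arm, and SAP 4.5.2 compares the groups with a rank test. The question is which date the window is counted from; the width of the window is a separate matter.

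**Working it through.** **Inputs.** Dose 4 at week 20 (Table 1). Sample 2 weeks later, ±3 days (SAP 3.1.2; protocol 7.1.2 and Table 5). Dose-4 windows of ±3 days (protocol 7.1.2) and -3/+7 days (protocol 6.1.5). Week-22 visit window of ±7 days (SAP 4.3). Eight participants per arm.

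**The plan's own figure.** Week 20 + 2 weeks = week 22; day 140 + 14 = day 154. With the boost on schedule the two clocks agree.

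**Planned-date reading.** Let S be the planned date of dose 4 and d the number of days by which the actual dose is late (negative if early).

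- SAP 3.1.2 window: S+14±3, that is S+11 to S+17.
- Protocol-compliant sample: S+d+14±3, that is S+d+11 to S+d+17 (7 possible days).
- An on-target sample at S+d+14 is inside the SAP window only if d lies between -3 and +3.
- Compliant days inside the SAP 3.1.2 window: 7 minus the absolute value of d, and never below 0.
- SAP 4.3 window: S+14±7, that is S+7 to S+21.

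| d (days) | Protocol-compliant days, from S | Day-14 sample inside SAP 3.1.2? | Compliant days inside SAP 3.1.2 | Compliant days inside SAP 4.3 |
|---|---|---|---|---|
| -3 | 8–14 | yes | 4 of 7 | 7 of 7 |
| 0 | 11–17 | yes | 7 of 7 | 7 of 7 |
| +1 | 12–18 | yes | 6 of 7 | 7 of 7 |
| +2 | 13–19 | yes | 5 of 7 | 7 of 7 |
| +3 | 14–20 | yes | 4 of 7 | 7 of 7 |
| +4 | 15–21 | no | 3 of 7 | 7 of 7 |
| +5 | 16–22 | no | 2 of 7 | 6 of 7 |
| +6 | 17–23 | no | 1 of 7 | 5 of 7 |
| +7 | 18–24 | no | 0 of 7 | 4 of 7 |

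A boost within the ±3 days of protocol 7.1.2 never pushes an on-target sample out. Deferrals of 4 to 7 days, which lie inside the window in protocol 6.1.5, do. At +7 days the two windows no longer overlap. Under the ±7 days of SAP 4.3, an on-target sample at +7 falls on S+21 and is still inside, so the SAP can call the same visit compliant in one section and out of window in another.

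**Dose-4 reading.** If 'scheduled final vaccination' just labels dose 4, both windows are days 11 to 17 after the actual dose, and 7 of 7 compliant days qualify whatever the delay. Naming the actual date in the SAP gives the same result.

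**Weight of one participant.** 1/8 = 12.5% of an arm.

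**The case against.** The strongest reply is that nothing conflicts. Elsewhere 'scheduled' labels planned doses rather than calendar dates: protocol 6.3 places the week-22 visit relative to the last scheduled immunisation, and protocol 10.4.1 and SAP 2.3 define per-protocol by receipt of every scheduled immunisation. On that usage the phrase distinguishes dose 4 from the last dose received by someone who stopped early, and SAP 3.1.2 agrees with the protocol. This stands as a fair reading. It is not the only one, because SAP 4.3 uses the word for a date. It also leaves a gap: a participant who never had dose 4 has no actual date, yet protocol section 9 asks withdrawn participants who have been immunised to undergo the week-22 procedures.

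Several stronger conclusions are tempting, and the documents do not support them:

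- *Any late boost puts the sample out of window.* Not for delays of 1 to 3 days with an on-target sample.
- *Small delays add up.* Three doses each 3 days late make 9 days only if the schedule is counted from enrolment. Footnote 6 counts from the preceding vaccination, so that example mixes two clocks.
- *A 14-day delay would centre the window on the boost itself.* The arithmetic is right (14 - 14 = 0), but such a delay lies outside both stated dose-4 windows. Falling short of the 4-week trigger does not make it compliant.
- *An earlier serum could become the primary value.* At d = 7 the week-21 sample would fall on S+14. But sera belong to named visits, protocol 7.1 marks week 22 as the primary endpoint, and the SAP provides for no substitution.
- *Out-of-window samples are lost.* The same sentence sends them to discussion, and protocol 10.4.2.1 has all samples processed.
- *The TMG would decide with titres in view.* The documents do not say so, and assay staff are blinded throughout.

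It is also true that protocol 2.2.1 calls the immunology primarily descriptive and not powered for comparison, which limits the stakes.

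**Conclusion.** The point holds as an ambiguity in day zero of the primary immunogenicity endpoint. A reader might infer an outright contradiction between SAP and protocol, but the usage of 'scheduled' elsewhere prevents that conclusion.

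Its size is conditional on the planned-date reading. A boost 4 or more days late puts an exact day-14 sample outside the SAP window, and at 7 or more days no compliant sample day qualifies. Inclusion is then discretionary, by a group whose clinical members know the allocation. That opens a route to bias without showing that any would occur. The documents give no expected number of deferred boosts, so the number of affected participants cannot be estimated. The change is worth making because the definition is primary and the correction is small.

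**What to change.** In SAP 3.1.2:

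1. State day zero as the actual date of the fourth vaccination.
2. Replace the TMG exception with a fixed rule: within the population already defined for immunogenicity (per-protocol in protocol 10.4.2.1), use the visit-10 (week 22) serum whatever its exact day. Add a sensitivity analysis limited to days 11 to 17 after the actual fourth dose.
3. Do not extend the rule to everyone who received dose 4. That would bring in participants who missed dose 2 or 3 and would change the analysis population.
4. Since SAP 2.3 plans both ITT and per-protocol analyses, say how participants without a fourth dose are handled in any ITT presentation. Also say whether an off-day sample alone counts as a major deviation, which SAP 2.3 leaves undefined.

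In the same edit, reconcile the ±7 days in SAP 4.3 and the 4 weeks in SAP 4.5.2 with this definition. The dose-4 windows in protocol 6.1.5 (-3/+7 days) and 7.1.2 (±3 days) also contradict each other and must be reconciled; no view is taken here on which is right.

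The SAP changes cost a few sentences and need no new data beyond the immunisation and visit dates already recorded on the CRF. Reconciling the dose windows is a separate protocol clarification.

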3.2. Secondary Endpoint

3.2.1. Safety

Any grade of adverse event, local to the ID and IM injection sites that start within 7 days after Doses 1-3.

3.3. Exploratory Endpoints

3.3.1. Immunogenicity

- Frequency and magnitude of HIV-gp140 specific B-cell-mediated responses in the systemic compartment measured by B-cell ELISPOT
- The magnitude of vaccine specific systemic T cell responses by T cell ELISpot assay
- The magnitude of antigen specific systemic IgA antibody responses ($\mu\text{g/ml}$)
- Frequency, titre and avidity of serum binding antibodies to other HIV Env antigens (alternative clades) by ELISA or other assays.
- Mapping of serum binding antibodies using Env subunit constructs (e.g., V2 scaffolds and hotspots) by ELISA.
- Frequency and magnitude of mucosal IgG and IgA antibody responses to CN54gp140 measured four weeks after the final immunisation.
- Frequency and titre of serum neutralising antibodies to homologous virus, and, if warranted a wider panel of viruses representing different clades.
- Frequency and magnitude of HIV-specific T-cell mediated responses measured by T-cell CFSE, and ICS (Intracellular Cytokine Staining).
- Frequency and magnitude of T-cell chemokine and cytokine release following ex-vivo antigen stimulation quantified by Luminex.
- Isolation and characterization of Env-specific monoclonal antibodies (IgG) from memory B cells in the systemic compartments (dependent upon elicited specific memory B-cell numbers).
- Characterisation of non-neutralising antibody function using ADCC/ADCVI, viral capture and aggregation assays.
- Epitope mapping of B- and T-cell responses.

3.3.2. Tolerability

- Pain scores at 0, 10 and 30 minutes following vaccination with EP

4. Statistical Analyses

Analyses of safety and tolerability endpoints for randomized participants will be performed at the MRC CTU at UCL. Immunogenicity data are not held at the CTU, and will be analysed elsewhere.

Adverse events and vaccine responses will be described as frequencies with 95% confidence intervals. Confidence intervals will be calculated using Wilson intervals, suitable for small sample sizes (table 3).

Table 3. Wilson intervals

Number of events	N=8		N=7		N=6		N=5	
	%	95% CI						
0	0%	0,32%	0%	0,35%	0%	0,39%	0%	0,43%
1	13%	2,47%	14%	3,51%	17%	3,56%	20%	4,62%
2	25%	7,59%	29%	8,64%	33%	10,70%	40%	12,77%
3	38%	14,69%	43%	16,75%	50%	19,81%	60%	23,88%
4	50%	22,78%	57%	25,84%	67%	30,90%	80%	38,96%
5	63%	31,86%	71%	36,92%	83%	44,97%	100%	57,100%
6	75%	41,93%	86%	49,97%	100%	61,100%		
7	87%	53,98%	100%	65,100%				
8	100%	68,100%						

4.1. Enrolment Description

The following numbers will be reported:

- Total volunteers screened
- Volunteers screened and
 - not randomised (with reason)
 - randomised
- Participants randomised with at least one immunisation by randomisation group.

A graphical representation (trial profile) will be prepared according to the CONSORT statement on publication of randomised clinical trials.

4.2. Baseline Characteristics

The baseline characteristics of the trial participants will be summarised by treatment group using appropriate summary statistics (mean and standard deviation for continuous normal variables, median and interquartile range for continuous non-normal variables, percentages for binary and categorical variables).

Baseline is defined as the date of the week 0 visit (day of randomisation), and for all variables the measurement is defined as the measurement on this day. If a measurement is not available on this day, the nearest measurement within 42 days prior to the week 0 visit will be used.

4.3. Follow-up Description

- The duration of follow-up, defined as the difference in weeks between the date of last contact with the volunteer and the date of randomisation, will be described in terms of median, IQR and range.
- The number of visits attended vs. the expected number of visits according to the number of participants randomised, by randomisation group.
- Loss to follow-up rate: the number (%) of participants not reaching 20 weeks will be described, indicating week last seen and the reason of loss to follow up.

Visit windows are defined as follows:

Immunisation visits at weeks 4 and 8 are compliant with the protocol if they take place ± 3 days from the scheduled date. Follow-up visits at weeks 1, 5 and 9 are compliant if ± 3 days, while follow-up at week 22 is compliant if ± 7 days from the scheduled date.

4.4. Interim Analysis

There is no planned interim analysis.

4.5. Primary Analysis

4.5.1. Safety

For each arm the proportion and its 95% CI will be reported for participants with a primary safety endpoint as defined in 3.1.1. The proportion with events will be compared in a pairwise manner between the three randomised groups, using Fisher's exact tests.

Grade 3 or above safety endpoints and any endpoints that lead to discontinuation of the vaccine regimen will be described, and a full listing of all events for each participant will be filed in the statistical master file.

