The AEs for the randomised subjects will be coded by MRC CTU staff using MedDRA. If a participant reports the same event more than once then the worst severity and worst relationship to trial vaccine will be taken. Discrepancies between diary card and CRF reports will be queried by the monitor if unclear. It is assumed that the grade assigned by the clinician is more accurate, and this will be the grade reported in the ITT analysis tables, prepared by MRC CTU. If the diary card grade is worse, this will be foot noted.

All safety end-points will be graded by the Clinical Investigators.

Safety outcomes for the randomised participants will be reported overall with proportion and 95% confidence interval, and by group and time-point, and by relationship to study product, and method.

For the primary ITT analysis of safety endpoints (as defined in **section 10.2**), results will be expressed as a proportion with confidence interval, and groups compared using Fisher's exact test.

Safety outcomes for the non-randomised participants will be reported separately.

10.4.5

Tolerability Outcomes

The tolerability data from the questionnaires will not be part of the SAP or reported in the Clinical Study Report.

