4.8. Subgroup Analysis

No subgroup analysis has been planned for this study.

A. Tables

Table 1 Doses received

Week	Group		
	ID/EP N=	IM/EP N=	IM/ID/EP N=
0	n (%)	n (%)	n (%)
4	n (%)	n (%)	n (%)
8	n (%)	n (%)	n (%)
20	n (%)	n (%)	n (%)

Table 2 Primary safety outcome, grade 3+ local or systemic solicited adverse event, or any event leading to treatment discontinuation.

	ID/EP (N=)	IM/EP (N=)	IM/ID/EP (N=)	Total (N=)
Participants with ≥ 1 event	n(%)	n(%)	n(%)	n(%)
Events per participant				
0	n			
1	n			
2	n			
3	n			
4	n			
≥ 5	n			
Total number of events	N	N	N	N
Type of event				
solicited local	n(%)			
solicited systemic	n(%)			
systemic	n(%)			
laboratory				
Grade of event				
1	n(%)			
2	n(%)			
3	n(%)			
4	n(%)			
Relationship to vaccine				
Definite	n(%)			
Probable	n(%)			
Possible	n(%)			
Unlikely	n(%)			
None	n(%)			

Description of any grade of local safety endpoints and any that lead to discontinuation of the vaccine regimen.

Table 3 Secondary safety outcome, AE local to injection site, within 7 days

	ID/EP	IM/EP	IM/ID/EP						
	Vaccine number								
	1	2	3	1	2	3	1	2	3
Total events									
Participants with ≥ 1 event									
Grade of event									
1									
2									
3									
4									

Table 4 Number of Solicited Adverse Events, by vaccination number

	ID/EP	IM/EP	IM/ID/EP						
	Vaccine number								
	1	2	3	4	1	2	3	4	
Total									
0									
1									
2									
3									
4									
≥ 5									
Per participant									
1									
2									
3									
4									
Per grade									
1									
2									
3									
4									

Table 5 Solicited adverse events, by type, grade and vaccination number

a) Local adverse event

Symptom	Maximum Grade	Group							
		Vaccination Number				n = number at risk			
		1 N=	2 N=	3 N=	4 N=	1 N=	2 N=	3 N=	4 N=
Discomfort	1								
	2								
	3								
	4								
Redness	1								
	2								
	3								
	4								
Swelling (soft)	1								
	2								
	3								
	4								
Induration (hard)	1								
	2								
	3								
	4								
Blisters	1								
	2								
	3								
	4								

b) Systemic adverse event

Symptom	Maximum Grade	Group							
		Vaccination Number				n = number at risk			
		1 N=	2 N=	3 N=	4 N=	1 N=	2 N=	3 N=	4 N=
Temperature	1 2 3 4								
Chills	1 2 3 4								
Myalgia	1 2 3 4								
Malaise	1 2 3 4								
Headache	1 2 3 4								
Nausea	1 2 3 4								

c) Systemic laboratory AEs

Symptom	Maximum Grade	Group							
		Vaccination Number				n = number at risk			

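### SAP 4.5.1 points to four primary safety items, but the table shell titled as the primary safety outcome covers three, and no shell gives a participant proportion for the fourth

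*SAP*

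**What the plan says.** SAP 3.1.1 introduces the primary safety endpoints with "Any of the following events occurring between week 0 and week 22 will be included in the analysis" and lists four items:

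1. grade 3+ local solicited AE;
2. grade 3+ systemic clinical or laboratory solicited AE;
3. AE of any grade that leads to a decision to stop immunisations;
4. "Any grade of adverse event within 7 days of receiving intradermal and standard intramuscular vaccinations with or without electroporation".

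SAP 4.5.1 then states: "For each arm the proportion and its 95% CI will be reported for participants with a primary safety endpoint as defined in 3.1.1". The three arms are compared in pairs by Fisher's exact test. The same section adds "Grade 3 or above safety endpoints and any endpoints that lead to discontinuation of the vaccine regimen will be described".

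The Appendix A Table 2 shell is titled "Primary safety outcome, grade 3+ local or systemic solicited adverse event, or any event leading to treatment discontinuation". A note after it reads "Description of any grade of local safety endpoints and any that lead to discontinuation of the vaccine regimen".

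Protocol 10.2.1.1 has the same four items as separate bullets. For the primary intention-to-treat analysis of safety endpoints (plural), Protocol 10.4.4 says "results will be expressed as a proportion with confidence interval, and groups compared using Fisher's exact test". Protocol 2.2.4 judges whether safety is unacceptable by the proportion of participants with a grade 3+ solicited AE or an event leading to discontinuation, which corresponds to items 1 to 3.

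**The concern.** The SAP describes its primary safety outcome in two ways. The text brings in all four items; the shell brings in three. The item left out is much the broadest, since it is not limited by grade, by site, or to solicited events.

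If one composite is meant, the choice changes the main safety figure for each arm. Once a participant has been counted for a mild AE in the 7-day window, a grade 3+ event in that participant adds nothing. A four-item proportion could therefore hide the three-item proportion that Protocol 2.2.4 relies on.

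If four separate endpoints are meant, a primary endpoint listed in the protocol has no place in the planned tables. The trial is open-label, so the choice is better settled in writing than when the tables are filled.

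**Working it through.** **1. The plan's own interval table.** SAP section 4 uses Wilson 95% intervals. With p = x/n and z = 1.96, the limits are

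[p + z²/2n ± z·√(p(1−p)/n + z²/4n²)] / (1 + z²/n).

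For n = 8, z²/n = 0.4802 and z²/2n = 0.2401.

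- 1/8: (0.125 + 0.2401)/1.4802 = 0.2467; half-width 1.96 × √(0.01367 + 0.01501)/1.4802 = 0.2242; interval 2.2% to 47.1%.
- 7/8: (0.875 + 0.2401)/1.4802 = 0.7533; same half-width; interval 52.9% to 97.8%.

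These match the SAP's printed 2 to 47% and 53 to 98%. All 30 intervals in the SAP's Wilson table reproduce to the rounded percent, so the table is not in question.

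**2. Items in 3.1.1 against the Appendix A shells.**

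| Shell | Content | Gives a participant proportion for item 4? |
|---|---|---|
| Table 2 | Items 1 to 3 | No |
| Table 3 | Local AEs within 7 days, separately for vaccines 1 to 3 (secondary endpoint) | No: local only, split by vaccine |
| Tables 4, 5 | Solicited AEs by vaccination | No: solicited only, split by vaccination |
| Tables 6, 7 | Duration of solicited events; those lasting over 7 days | No |
| Tables 8, 9 | Non-solicited AEs | No: no 7-day window |
| Table 10 | Pain scores around electroporation (EP) | No |

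Item 4 cannot be put together from Tables 3, 4 and 8, because the same participant can appear in several of them and Table 8 has no time window.

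Two features of Table 2 might seem to bring item 4 in. The grade 1 and 2 rows do not: under the table's title they can be filled by AEs that led to discontinuation. The note after the table promises a description of local endpoints, not a proportion of participants with any AE.

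**3. What the difference can do on the composite reading (assumed counts).** Take one arm of 8 in which 7 participants have some AE within 7 days, and those with an item 1 to 3 event are among the 7.

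| Participants with items 1–3 | Proportion by the text (items 1–4) | Proportion by the shell (items 1–3) |
|---|---|---|
| 1 | 7/8 = 87% (53–98%) | 1/8 = 13% (2–47%) |
| 3 | 7/8 = 87% (53–98%) | 3/8 = 38% (14–69%) |

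The percentages are those in the SAP's Wilson table. The four-item figure stays the same while the number with items 1 to 3 triples.

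**4. How common item 4 might be.** The documents give no rate for this trial. Assume an AE in 30% to 50% of 7-day windows.

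- Four windows (Doses 1 to 4), independent: 1 − 0.7⁴ = 76% to 1 − 0.5⁴ = 94% of participants.
- Three windows (Doses 1 to 3), independent: 1 − 0.7³ = 66% to 1 − 0.5³ = 88%.
- Windows perfectly correlated: 30% to 50%.

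Whether Dose 4 counts is unclear. Item 4 speaks of intradermal and standard intramuscular vaccination with or without EP, while Dose 4 is intradermal protein alone.

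**The case against.** Several points on the other side have force.

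- **No composite is declared.** Neither document uses the word. The lead-in to 3.1.1 says what enters the analysis, not that one variable is formed. The protocol's four bullets and its plural wording allow an item-by-item reading. A reader might infer that the SAP definitely sets a four-item composite; the documents do not settle this. On the item-by-item reading there are no rival headline figures. There is a missing row, and a Table 2 that pools three endpoints at participant level. Its type-of-event rows separate local, systemic and laboratory events, but they sit under the total number of events and so appear to count events, and discontinuation has no row.
- **The shells are not exhaustive.** Table 2 has no columns for the interval or test that 4.5.1 requires, and Table 5b omits vomiting, a listed solicited event. A missing row does not prove that item 4 would go unreported, because 4.5.1 still commits to 3.1.1 endpoints. This stands, but it does not tell the analyst what belongs under the title of Table 2.
- **A ceiling is not shown.** A reader might infer that the four-item proportion must be close to 100% where EP is used, since Protocol 2.2.2.3 reports pain at EP in nearly every recipient of the intramuscular device and lists it as an adverse reaction. But Protocol 7.4.8 scores that pain in a separate tolerability questionnaire, and whether it enters the AE data is not stated. More lasting local reactions are called common, without a rate. The assumed rates above span 30% to 94%.
- **The stakes are modest.** Protocol 10.3 and SAP 2.2 disclaim confident group comparisons, and Protocol 2.2.4 already uses the narrower criterion. A reader might infer that safety information would be lost. It would not: 4.5.1 describes grade 3+ and discontinuation events and files a full listing of all events.

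**Conclusion.** The mismatch is real and should be fixed, but it is limited in size. It holds on either reading of 3.1.1. As a composite, text and shell define different primary proportions from the same data. Item by item, the fourth primary endpoint has no participant-level row and the other three appear only pooled at that level.

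That conclusion rests on the wording of SAP 3.1.1, 4.5.1 and Appendix A and needs no assumption about event rates. The 87% against 13% contrast does: it takes the composite reading and assumed counts, and it illustrates the possible gap without predicting it. The case for change is a clear and interpretable primary safety figure. It is not power, and it is not recovery of missing data.

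**What to change.** In SAP 3.1.1 and 4.5.1:

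- State that the Table 2 proportion is items 1 to 3: grade 3+ solicited AE, or discontinuation because of an AE. This matches Protocol 2.2.4.
- Report item 4 as a separate primary safety endpoint, not pooled with items 1 to 3, with its own participant-level row, Wilson interval and pairwise Fisher tests.
- State whether item 4 includes the window after Dose 4, and whether momentary pain at EP, scored in the tolerability questionnaire, counts as an AE.
- Make the shells match, add the intervals and tests that 4.5.1 requires, and label the tests as unadjusted and descriptive.
- Show the three components of Table 2 as participant-level counts without further tests, and say that items 1 to 3 are tested pooled.

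Cost: SAP wording and a few table rows, with no new data. Two proportions by three pairs makes 6 Fisher tests, against 3 (one proportion by three pairs) on the composite reading and 12 (four by three) item by item. The price is three more unadjusted tests than the composite reading, and no separate test for each of items 1 to 3.
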